5.1 Schedule of Assessments

The schedule of assessments is presented in table format in the study synopsis

Study Phase	Screening	Treatment														
		1	2	3	4	5	6	7	8	9	10	11	12	13	14	15
VISIT NUMBER	0	1	2	3	4	5	6	7	8	9	10	11	12	13	14	15
WEEK	0	1	2	3	4	5	6	7	8	9	10	11	12	13	14	15
Informed consent	X	X														
Study drug		X	X	X	X	X	X	X	X	X	X	X	X	X	X	X
Study drug Instruction		X														
Medical history ²	X ²	X ²			X ²				X ²				X ²			
Physical examination ³	X ³	X ³			X ³				X ³				X ³			
Adverse Event		X			X				X				X			
Record concomitant medications ⁴	X	X			X				X				X			
Vital signs ⁵	X	X			X				X				X			
CBC w/ differential, platelet count	X	X			X				X				X			
Comprehensive Metabolic Panel (CMP)	X	X			X				X				X			
Urinalysis and Urine protein/creatinine	X	X														
Urine Pregnancy test ⁷	X	X			X				X				X			
HBsAg, HBcAb, HCV**Not required if collected 6 months prior to screening	X															
Serum immunoglobulin levels (IgM, IgE, IgG)	X	X														
Serum IgG subclasses	X	X			X				X				X			
C3 and C4	X															
Mechanistic samples	X	X			X								X			
Fasting lipid profile	X	X			X				X				X			
CT chest, abdomen, pelvis ⁸	X															
IgG4-RD RI	X	X			X				X				X			
Physician Global Activity VAS	X	X			X				X				X			
Symptom Severity Index	X	X			X				X				X			
Glucocorticoid Toxicity Index	X	X			X				X				X			
SF-36 Health Survey	X	X			X				X				X			

Study Phase											
VISIT NUMBER	6				7				8	9	10/EO
WEE	16	17	18	19	20	21	22	23	24	28	36
Informed consent											
Study drug administration	X	X	X	X	X	X	X	X	X		
Medical history ²	X				X ²				X	X ²	X ²
Physical examination ³	X				X ³				X	X ³	X ³
Adverse Event assessment ⁴	X				X				X	X	X
Record concomitant medications ⁴	X				X				X	X	X
Vital signs ⁵	X				X				X	X	X
CBC w/ differential, platelet	X				X				X	X	X
Chemistry Panel	X				X				X	X	X
Urinalysis and Urine protein/creatinine											X
Urine Pregnancy test ⁷	X				X				X	X	X
HBsAg, HBcAb, HCV ^o											
Serum immunoglobulin levels (IgM, IgE, IgG)									X		X
IgG subclasses	X				X				X		X
C3 and C4											X
Fasting lipid profile	X				X				X		X
Mechanistic samples									X		
IgG4-RD RI	X				X				X		X
Physician Global Activity VAS	X				X				X		X
Symptom Severity Index	X				X				X		X
Glucocorticoid Toxicity Index	X				X				X		X
SF-36 Health Survey	X				X				X		X

¹The Screening visit (Visit 1) and the Treatment Week 1 (Visit 2) visit could potentially be on the same day

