5.2 Study Assessments

Screening Visit

The following procedures will be performed:

1. Obtain written informed consent after consent presentation
2. Obtain Medical history
 - a) Including demographics
 - b) Including history of IgG4-RD
3. Physical examination
4. Record concomitant medication
5. Vital signs including; BP, P, R, T, weight, and height.
 - a. Weight will be measured with outerwear and shoes removed
 - b. Height will be measured with shoes removed (screening visit only)
 - c. Blood pressure and pulse rate obtained after the subject has been supine ≥ 5 minutes
6. Adverse Event monitoring (from time of study drug administration)
7. Laboratory tests:
 - a. CBC with cell differential and platelets
 - b. Chemistry panel
 - c. Urinalysis and urine protein/creatinine ratio
 - d. Urine pregnancy test (only for woman of child bearing age)
 - e. Hepatitis B and C tests (not required if collected 30 days prior to screening visit)
 - f. Serum Immunoglobulin levels (IgM, IgE, IgG)
 - g. Serum IgG4 subclasses
 - h. Complement levels
 - i. Fasting lipid profile
 - j. Mechanistic samples will be collected from subject at weeks 0, 1, 4, 12 and 24 studies)
8. Imaging tests: CT chest, abdomen, pelvis
9. Physician reported outcomes
 - a. IgG4 Responder Index (IgG4-RD RI)
 - b. Physician Global Activity VAS
10. Patient reported outcomes
 - a. Symptom Severity Index
 - b. Glucocorticoid Toxicity Index
 - c. SF-36 Health Survey
 - d. Patient Global Activity VAS

Baseline Visit: Visit 2 (week 1)

The screening (visit 1) and baseline visit (visit 2) could potentially be combined and completed on the same day

The following procedures will be performed:

1. Verify eligibility criteria.
2. Review general medical and IgG4 history
3. Brief physical examination
4. Record concomitant medication
5. Vital signs including; BP, P, R, T, weight, and height.

- a. Weight will be measured with outerwear and shoes removed
- b. Blood pressure and pulse rate obtained after the subject has been supine ≥ 5 minutes
6. Adverse Event monitoring
7. Laboratory tests:
 - a. CBC with cell differential and platelets
 - b. Chemistry panel
 - c. Urinalysis and urine protein/creatinine ratio
 - d. Urine pregnancy test (only for woman of child bearing age)
 - e. Serum Immunoglobulin levels (IgM, IgE, IgG)
 - f. Serum IgG4 subclasses
 - g. Fasting lipid profile
 - h. Mechanistic samples will be collected from subject at weeks 0, 1, 4, 12 and 24 studies)
8. Patient-reported outcomes:

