 - a. Symptom Severity Index
 - b. Glucocorticoid Toxicity Index
 - c. SF-36 Health Survey
 - d. Patient Global Activity VAS
9. Physician-reported outcomes
 - a. Glucocorticoid Toxicity Index
 - b. Physician global activity VAS
 - c. IgG4-RD RI
10. Study drug administration and teaching
11. Study medication dispense

Visit 3 (week 4)-visit 10 (week 36)

Patients will have visits at Weeks 4, 8, 12, and then every 4 weeks per the schedule of assessments shown in Table 1

1. Brief physical exam including vital signs (Full physical exam at EOS)
2. Assessment of signs and symptoms of IgG4-RD
3. Concomitant Medications review
4. Adverse Events Assessments
5. Assessment of signs and symptoms of IgG4-RD activity
6. Abatacept administration (baseline, w4, w12, w20, w28, w36, w44)
7. Laboratory tests (to be drawn before study product administration). See schedule of events.
 - i. Mechanistic samples will be collected from subject at weeks 0, 1, 4, 12 and 24 studies)
8. Patient-reported outcomes (per schedule of events, table 1)
9. Physician reported outcomes (per schedule of events, table 1)
10. Study medication accountability and dispense

Safety follow up visit (if needed)

During the safety follow up the following procedures will be completed

1. Vital signs and Physical exam
2. Concomitant Medications review

3. Adverse Events Assessments
4. Assessment of signs and symptoms of IgG4-RD

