7.2 Efficacy Assessments

The following efficacy assessments will be performed according to the time points defined in the Schedule of Assessments (Table 1).

- **IgG4-RD Responder Index**

Disease activity will be measured per schedule of assessments. For determination of the IgG4-RD responder index as described in the schedules of assessments (IgG4-RD RI), the following criteria will be used (modified after Carruthers et al. 2012): Organ site, symptomatic, urgent disease (as per IgG4-RD RI) over the previous 28 days.

The original IgG4-RD RI has been modified to include the full spectrum of organs affected

most frequently by IgG4-RD and to eliminate serum IgG4 concentrations as part of the instrument. In addition, an assessment of damage caused by IgG4-RD in each affected organ is included. A sample assessment form is included in [Appendix](#).

- **Physician Global Disease Activity VAS**

The physician's overall assessment of the subject's current disease activity will be recorded on a 100 mm linear horizontal VAS, where the left hand extreme of the line is considered "Very Good" (symptom free and no IgG4-RD symptoms) and the right-hand extreme is considered "Very Bad" (maximum IgG4-RD activity).

Details on the efficacy assessments can be found in [Appendix](#).

- **Subject's Global Disease Activity VAS**

The subject's overall assessment of the subject's current disease activity will be recorded on a 100 mm linear horizontal VAS, where the left hand extreme of the line is considered "Very Good" (symptom free and no IgG4-RD symptoms) and the right hand extreme is considered "Very Bad" (maximum IgG4-RD activity).

- **Symptom Severity Index**

The Symptom Severity Index is a novel instrument for assessing patient-reported disease severity. It has not yet been validated in a longitudinal study of patients with IgG4-RD but is based on similar instruments used in other conditions like diabetes mellitus, hypertension, and benign prostate hypertrophy. The instrument queries patients on symptoms that can be associated with different manifestations of IgG4-RD. For each organ, the patient scores the severity of his/her symptoms and a total score is then derived. In addition to helping assess the efficacy of treatment, data collected through the use of this instrument in this trial will be used to assess the validity of the instrument.

- **Glucocorticoid Toxicity Index**

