8.3 Quality of Life Assessments

Quality of life assessments will include the Physician Global Disease Activity Assessment Visual Analogue Scale (PhGA VAS), the Patient Global Disease Activity Assessment VAS (PtGA VAS), the Symptom Severity Index and the 36-item short form health survey (SF-36). Unless otherwise specified, the QOL analyses will include all randomized subjects who have a non-missing baseline and at least one post-baseline QOL assessment. Subjects in this subset

will be analyzed according to their randomized treatment assignment, regardless of treatment received.

The percentage of participants randomized to each treatment group who complete the QOL questionnaires at each assessment point after baseline (i.e., QOL completion rates) will be calculated and compared. If significant differences in QOL completion rates are observed, additional analyses may be performed to evaluate the potential for reporting biases.

For each QOL endpoint, descriptive statistics will be presented for recorded values at each visit, including mean, standard deviation, median, minimum, maximum, change from baseline and percent change from baseline.

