4. **Do not calculate the score. This will be done by your physician.**

Example:

Symptom	1.) Frequency (Check one)				2.) How much distress does the symptom cause you? (Check one)					Score
	Never (0)	A few days a month (1)	A few days a week (2)	Every Day (3)	None (0)	A little bit (1)	Some- what (2)	Quite a bit (3)	Very much (4)	
Swelling of salivary glands under or side of the jaw				X			X			8
Dry mouth	X									
Swelling around the eyes	X									
Change in vision			X			X				3

IgG4-Related Disease Symptom Distress Index

Symptom	Frequency (Checkone)				How much distress does the symptom cause you? (Checkone)					Score
	Never	A few days a month	A few days a week	Every Day	None	A little bit	Some-what	Quite a bit	Very much	
	(0)	(1)	(2)	(3)	(0)	(1)	(2)	(3)	(4)	
Salivary Glands										
Swelling of salivary glands under or side of the jaw										
Dry mouth										
Orbit (Eye Area)										
Swelling around the eyes										
Change in vision										
Dry eyes										
Other Head and Neck										
Sinus congestion/discharge										
Sinus pain										
Loss of sense of smell										
Chest										
Shortness of breath										
Cough										
Abdomen										
Pain in the abdomen										
Loss of appetite										
Nausea and/or vomiting										
Loose stool and/or diarrhea										

Symptom	Frequency (Checkone)				How much distress does the symptom cause you? (Checkone)					Score
	Never (0)	A few days a month (1)	A few days a week (2)	Every Day (3)	None (0)	A little bit (1)	Some-what (2)	Quite a bit (3)	Very much (4)	
Genitourinary (male only)										
Pain in the groin										
Difficulty starting a urinary stream										
Urinating frequently										
Waking up at night to urinate										
Skin and Extremities										
Yellowing of the skin										
Swelling of the lower legs										
Other Symptoms										
1.										
2.										
3.										
Total Scores										

Of all the symptoms listed above, which three do you consider to be the most bothersome, severe, or important to you?

- 1.
- 2.
- 3.

Patient Survey (Subject should complete this form)

Instructions: Please rate your overall health related to your IgG4-Related Disease in the past week by selecting a whole number below, using the following scale: 1 = Extremely Poor and 10 = Excellent.

*Health problems due to a disease other than IgG4-related Disease should not be considered in this evaluation.

PARTICIPANT GLOBAL ASSESSMENT

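### The patient global disease activity VAS is scheduled only at screening and baseline, so the change from baseline planned in section 8.3 has no follow-up data

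*Protocol*

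**What the plan says.** Four parts of the protocol bear on this measure.

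- **Role.** Section 7.1 includes the subject's global disease activity VAS in the assessments used to follow disease activity. Section 8.3 names the patient global VAS (PtGA VAS) as a quality-of-life assessment and states: "For each QOL endpoint, descriptive statistics will be presented for recorded values at each visit". The statistics it then lists include change and percent change from baseline.
- **Timing in the visit lists (5.2).** The screening list (item 10) and the baseline list (item 8) both carry "d. Patient Global Activity VAS". The combined list for visits 3 to 10 itemises no patient-reported instrument and says only "Patient-reported outcomes (per schedule of events, table 1").
- **Timing in the efficacy section (7.2).** "The following efficacy assessments will be performed according to the time points defined in the Schedule of Assessments (Table 1").
- **The schedule (5.1).** In both halves of the table the only global rating is "Physician Global Activity VAS". The Symptom Severity Index, Glucocorticoid Toxicity Index and SF-36 have their own rows; a patient global does not.

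The instrument itself is defined. Section 7.2 and Appendix C describe a 100 mm line for current disease activity, "where the left hand extreme of the line is considered" very good and the right-hand end very bad, so a higher value is worse. After the symptom questionnaire, Appendix E also prints a Patient Survey with a participant global rating of overall health over the past week, "using the following scale: 1 = Extremely Poor and 10 = Excellent".

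**The concern.** A change from baseline needs at least one later value on the same instrument. Here the baseline value is requested by name, but both provisions that could call for a later one (5.2 for visits 3 to 10, and 7.2) refer to a table that omits the measure. A site that follows the protocol exactly would collect two early values per subject, or one if screening and baseline are combined, and then stop.

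What would be lost is the follow-up of the only patient rating of disease activity as such; the other patient-reported instruments cover symptoms and general health. This is not something to leave to an analysis plan, which can define how data are summarised but cannot add a collection that the protocol did not schedule.

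**Working it through.** No sample size, power or error rate is involved. The check is a count of scheduled assessments per instrument.

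**Step 1: which table is meant.** Section 5.1 says the schedule appears in the synopsis, but the only schedule printed in the text follows section 5.1 itself. I take that as Table 1.

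**Step 2: the count.** Visits after baseline fall at weeks 4, 8, 12, 16, 20, 24, 28 and 36, which is 8 visits. Week 28 has no mark for any of the instruments below, so the relevant denominator is 8 − 1 = 7.

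| Instrument | Screening | Baseline (week 1) | Weeks 4, 8, 12 | Weeks 16, 20, 24 | Week 28 | Week 36 | Post-baseline total |
|---|---|---|---|---|---|---|---|
| Physician global VAS | yes | yes | 3 | 3 | 0 | 1 | 7 |
| Symptom Severity Index | yes | yes | 3 | 3 | 0 | 1 | 7 |
| SF-36 | yes | yes | 3 | 3 | 0 | 1 | 7 |
| Patient global VAS | yes (5.2 only) | yes (5.2 only) | 0 | 0 | 0 | 0 | 0 |

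With about 10 subjects, the schedule yields up to 10 × 7 = 70 post-baseline values for each of the first three instruments and 10 × 0 = 0 for the patient global VAS.

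**Step 3: is there another route to a follow-up value?** Section 5.6 asks subjects who withdraw early to have the assessments listed for the end-of-study visit. That column of the schedule has no patient global either, so withdrawal visits add nothing.

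**Step 4: could the row have been lost in reading the PDF?** It is absent from both halves of the table, while the neighbouring rows are intact in both. Loss of the same single row twice is unlikely.

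**Step 5: what section 8.3 can then report.** Baseline values can be summarised. Values at later visits, change and percent change cannot, because no scheduled follow-up value exists.

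**The case against.** The strongest reply is that this is a clerical slip with little riding on it. The patient global is absent from the study objectives, from the endpoints in the synopsis and section 8.2, and from the synopsis list of disease activity parameters. The global assessment named as a secondary endpoint is the physician's, and that one is scheduled. Section 8.3 plans only descriptive summaries, in about 10 open-label subjects. Section 7.1 also shows an intention to follow the measure over time, so site staff might collect it anyway. All of this stands and limits the severity. It does not supply a scheduled visit.

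Two stronger readings are tempting, and the protocol does not support them.

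- **That the 1-10 item in Appendix E takes over after baseline, so that improvement could appear as worsening.** The item does run in the opposite direction, with a different range, recall period and construct. With assumed values, a baseline of 60 mm followed by a rating of 8 multiplied up to 80 would give 80 − 60 = +20, an apparent worsening. Reversed and rescaled, the rating is (10 − 8)/9 × 100 = 22.2, a change of −37.8. But this requires mixing the two scales, which the protocol nowhere instructs. Section 8.3 names a VAS, and the Appendix E item is not one. The protocol gives that item no visit and no analysis role. If it accompanies the symptom form, and if that form is the Symptom Severity Index of the schedule, it would also be collected at screening and week 1. It would then have its own baseline and a consistent sign.
- **That the quality-of-life analysis set would be empty.** Section 8.3 asks for a baseline and at least one post-baseline quality-of-life assessment. Other instruments, such as the SF-36, can meet that condition. Only the patient global VAS lacks follow-up.

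**Conclusion.** The point holds as an internal inconsistency: the protocol plans a change from baseline for the patient global VAS and schedules 0 of the 7 post-baseline assessments that its companion instruments receive. The planned change and percent change cannot be computed from the schedule as written.

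Severity is minor. No primary or secondary endpoint in section 8.2 depends on the measure. The conclusion rests on two assumptions: that the table printed under section 5.1 is the Table 1 to which sections 5.2 and 7.2 refer, and that its rows were read completely.

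The second patient global item in Appendix E is a matter for tidying, not a demonstrated error. It matters only because two patient global items are printed and the protocol does not say how they relate.

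**What to change.** 1. Add a row for the "Patient Global Activity VAS" to the schedule in section 5.1 at the visits where the Symptom Severity Index is marked: screening, week 1, and weeks 4, 8, 12, 16, 20, 24 and 36. Identify it in the row or a footnote as the 100 mm scale of Appendix C, with higher values worse. That gives 7 post-baseline values per subject and makes the section 8.3 summaries possible.
2. Remove the 1-10 participant global item from Appendix E. Alternatively, label it as a separate overall-health item (higher is better), state when it is collected, and state that it is not used as the PtGA.

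The cost is one schedule row and one appendix edit, plus one VAS line at visits where the subject already completes other questionnaires. For about 10 subjects that is at most 10 × 7 = 70 extra single-line ratings over the whole trial. The change helps only visits that take place after it comes into force.

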5.3 Discussion of Study Design

No therapies for IgG4-RD have been approved by regulatory authorities and thus there are no established study designs for this disease indication. This study design is consistent with the focus of this trial on proof-of-concept and mechanistic studies and will be suitable to achieve this goal based on the strict primary outcome criteria. There is no control group in this proof of concept study. The design will be able to assess whether abatacept can have an effect on disease response as has been shown in a prior case report as discussed above. The design of this trial is appropriate to our current understanding of the potential role of abatacept in IgG4-RD, which is presently too limited to justify a randomized trial. Should patients fail to respond to the study drug abatacept or should they develop end-organ manifestations, they will be able to obtain standard of care glucocorticoid treatment.

A washout period is built into the study protocol. Exclusion criteria include the prior use of rituximab (or other B cell depleting agents) within 6 months of enrollment unless B cells have been demonstrated to have repopulated or the use of any investigational agent within 5 half-lives of the agent (or 6 months if the half-life is unknown) prior to enrollment. This should be sufficient in identifying any adverse effects due to the investigational product abatacept. However, patient's may have been on glucocorticoids during trial entry, but must be willing to taper off of glucocorticoids within ~~4~~ 8 weeks of beginning abatacept. This is necessary in order to sufficiently recruit patients for the study.

The investigational medication abatacept is dosed weekly by subcutaneous route which is consistent with its pharmacokinetic and pharmacodynamic profile. It is approved for the treatment of rheumatoid arthritis at this dosing interval. These medications may be continued indefinitely for control of the disease and any effect should be seen within 24 weeks of treatment.

5.4 Early Termination of the Study

If the Investigator or the Sponsor becomes aware of conditions or events that suggest a possible hazard to subjects if the clinical study continues, then the clinical study may be terminated after appropriate consultation among the involved parties. The clinical study may be terminated at the Sponsor's discretion also in the absence of such a finding.

Conditions that may warrant termination of the clinical study include, but are not limited to:

- The discovery of an unexpected, relevant, or unacceptable risk to the subjects enrolled in the clinical study;
- Failure to enroll subjects at the required rate;
- A decision of the Sponsor to suspend or discontinue development of the IMP.

Should the study be terminated, and/or the site closed for whatever reason, all documentation pertaining to the study and IMP must be returned to the Sponsor. Any actions required for assessing or maintaining study subject safety will continue as required, despite termination of the study by the Sponsor.

End-of-Study is defined as completion of the End-of-Study Visit on Week 36.

5.5 Selection of Study Population

Male and female subjects who meet the ACR/EULAR 2018 Classification Criteria for IgG4-RD AND active disease (defined by IgG4-RD RI ≥ 2 at screening with disease manifestation in at least one organ system excluding lymph nodes at screening). Subjects are not required to have failed prior therapy for their disease to be eligible for this study.

Inclusion Criteria

Subjects who meet the following criteria will be considered eligible to participate in the clinical study if they:

2. Are male or female 18 years of age or older
3. Meet the ACR/EULAR 2018 Classification Criteria for IgG4-RD (see appendix)
4. Have active disease based on an IgG4-RD RI ≥ 2 at screening with disease manifestation in at least one organ system excluding lymph nodes at screening
5. May or may not have received prior IgG4-RD therapy
6. Must be willing to taper off any systemic corticosteroid therapy within 4 8 weeks of first dose of trial drug.
7. Must be able and willing to discontinue any immunosuppressive agent at screening (e.g. methotrexate, mycophenolate mofetil, 6-mercaptopurine, tacrolimus, cyclophosphamide or azathioprine).
8. No history of severe allergic reactions to monoclonal antibodies.
9. Are able and willing to complete the entire study according to the study schedule.
10. Are willing to forego other forms of experimental treatment during the study.
11. Are able to provide written informed consent.

Exclusion Criteria

Subjects who meet one or more of the following criteria will not be considered eligible to participate in the clinical study:

1. History or evidence of a clinically unstable/uncontrolled disorder, condition or disease (including but not limited to cardiopulmonary, oncologic, renal, hepatic, metabolic, hematologic or psychiatric) other than IgG4-RD that, in the opinion of the Investigator, would pose a risk to patient safety or interfere with the study evaluation, procedures or completion.
2. Malignancy within 5 years (except successfully treated in situ cervical cancer, resected squamous cell or basal cell carcinoma of the skin, or prostate cancer with no recurrence ≥ 3 years following prostatectomy).
3. Liver disease: Acute or chronic non-IgG4-related liver disease deemed sufficiently severe to impair their ability to participate in the trial.
4. Uncontrolled disease: evidence of another uncontrolled condition, including drug and alcohol abuse, which could interfere with participation in the trial according to the protocol.
5. Presence of recurrent or chronic infections, defined as ≥ 3 infections requiring antimicrobials over the past 6 months prior to screening.

6. Active infection requiring hospitalization or treatment with parenteral antimicrobials within the 30 days prior to randomization.
7. Prior use of rituximab (or other B cell depleting agents) within 6 months of enrollment unless B cells have been demonstrated to have repopulated.
8. Use of any investigational agent within 5 half-lives of the agent (or 6 months if the half-life is unknown) prior to enrollment.
9. White blood cell count $< 2.5 \times 10^3/\mu\text{L}$.
10. Absolute neutrophil count (ANC) $< 1.0 \times 10^3/\mu\text{L}$.
11. IgG4-related renal disease with serum creatinine $> 2.0 \text{ mg/dL}$.
12. Hemoglobin $< 10 \text{ g/dL}$.
13. Platelet count $< 75 \times 10^9/\text{L}$.
14. Known positive result for HIV I or II antibody, hepatitis B surface antigen, hepatitis B core antibody or hepatitis C antibody.
15. Has received live vaccines within 4 weeks of enrollment.
16. Inability to communicate reliably with the investigator.
17. Patient is pregnant or breast feeding, or planning to become pregnant while enrolled in the study, up to EOS visit.
18. Positive pregnancy test at screening or during the study.
19. Subjects of childbearing potential who do not agree to use medically acceptable methods of contraception.
20. Known or suspected sensitivity to mammalian cell-derived products or any components of the study drug.
21. History of alcohol and/or substance abuse within 12 months prior to screening.
22. Unable or unwilling to partake in follow-up assessments or required protocol procedures.

